# AIM 1: Determine the impact of timed rectal evacuation on anorectal dysfunction in MS patients

We will conduct a four week, single-center, randomized, double-blind placebo controlled clinical trial designed to assess the efficacy of timed rectal evacuation in improving the subjective global assessment of bowel symptoms in a cohort of patients with mild-to-moderate severity MS disease. Patients will be randomized 1:1 to administer either placebo or bisacodyl 10 mg rectal suppositories every other day during the 4 week trial. The primary endpoint will be the change in patients' rating of bowel symptom severity (10 point rating scale) at end of 4 weeks compared to baseline values. We will define an adequate treatment response as greater than a 30% reduction in symptom severity using an intention-to-treat analysis.

AIM 2: Determine the predictors of treatment response and impacts on quality of life

We plan to collect information on the patients' assessed severity of baseline and treatment-associated anorectal dysfunction, their impact on quality of life, as well as daily bowel diaries. Patients also will undergo anorectal sensory and manometric testing as a part of their routine clinical care. Enrolled patients that complete the study will be assessed for study medication compliance. All of these measures will be used to explore factors that are associated with treatment response. Changes in assessments of anorectal dysfunction-related quality of life will serve as key secondary end-points.

This proposal will significantly advance MS care and management by developing the evidence to support the adoption of a simple, safe, and cost-effective clinical treatment algorithm for anorectal dysfunction in the MS population. This paradigm for anorectal dysfunction management could be applicable to a majority of MS patients, and the treatment algorithm could be introduced to patients by nurses or mid-level clinical providers during points of routine MS patient care. Importantly, the treatment could be effectively accomplished by most patients and their caregivers at home. The findings of this investigation could also have a broader influence on care models for anorectal dysfunction associated with a range of other neurological illnesses, such as Parkinson's Disease, ALS, or stroke.

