Finally in Phase 3, after the 4 week study period, patients will meet with the study coordinator to collect unused study medication and completed bowel diaries, and then undergo final reassessments of bowel dysfunction severity and QOL measures. This process could take up to 1 hour. After the questionnaires are completed, patients and the PI/Co-PI will be debriefed (i.e. study arm allocation will be revealed) before having a routine followup clinic visit (continuity of care).

- 1) The study coordinator will identify and screen potential study subjects (by accessing the "UPMC Multiple Sclerosis and Related Disorders Registry" (PRO12010609) to identify prospective subjects), coordinate the informed consent process with the PI/Co-PI, collect intake questionnaires, and provide instruction on bowel diaries (Phase 1). The coordinator will schedule referrals for anorectal function testing and follow-up DDC visit, and contact patients during the 4-week trial period to verify compliance. Finally, the coordinator will collect bowel diaries and remaining medications at study end, administer study exit questionnaires, and then debrief subjects and the PI/Co-PI once the blind is broken (Phase 3).
- 2) DDC GI nursing staff routinely performs HRAM studies and will do so in this study. The PI/Co-PI will be involved in clinical care and recommendations both during Phase 2 and Phase 3 (and beyond).
- 3) MS Physicians will be involved in initial identification of potential subjects and all MS-related continuity of care.
- 4) Falk Pharmacy serves UPMC for clinical trials, and staff will ensure the 1:1 randomization and distribution of either twenty placebo or biscodyl 10 mg rectal suppositories (used every other day over 4 weeks during the study period). Falk Pharmacy staff is experienced in running clinical trials and maintaining double-blind study conditions between subjects and investigators. Patients will receive a slight excess number of suppositories in order to assess study medication compliance at trial end.

STUDY MEASURES: We plan to obtain the following information from all enrolled patients:
1) Primary Patient-Reported Outcome Measure: "Using a scale of 1 to 10 (1 being no problem and 10 being maximally impactful symptoms), how would you rate the severity of your bowel symptoms over the past 2 weeks?"

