- 2) Daily Bowel Diaries patients will record the consistency (Bristol Stool Scale, 1-7), number of bowel movements (BM), and occurrence of any fecal incontinence (FI) episodes each day. This data will be used to abstract BM and FI weekly frequency, as well as the mean change in stool consistency during the study period.
- 3) Patient Assessment of Constipation Symptom Questionnaire (PAC-SYM)
- 4) Fecal Incontinence Severity Index (FISI)
- 5) Patient Assessment of Constipation QOL (PAC-QOL)
- 6) Rockwood Fecal Incontinence Quality of Life Scale (FIQL)
- 7) SF-36 health status questionnaire
- 8) Study Medication Compliance
- 9) Anorectal Sensory and High Resolution Anorectal Manometry Testing: First sensation of rectal filling, urgency, and pain, basal anal resting pressure, voluntary anal squeeze pressure, and the rectal-anal inhibitory reflex (RAIR) to rectal distention and simulated strain, as well as the ability to evacuate a 50 cc volume rectal balloon within one minute.

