#### SECONDARY END POINTS:

1) Daily Bowel Diaries – patients will record the consistency (Bristol Stool Scale, 1-7), number of bowel movements (BM), and occurrence of any fecal incontinence (FI) episodes each day. This data will be used to abstract BM and FI weekly frequency, as well as the mean change in stool consistency during the study period.

- 2) Patient Assessment of Constipation Symptom Questionnaire (PAC-SYM)
- 3) Fecal Incontinence Severity Index (FISI)
- 4) Patient Assessment of Constipation QOL (PAC-QOL)
- 5) Rockwood Fecal Incontinence Quality of Life Scale (FIQL)
- 6) SF-36 health status questionnaire
- 7) Study Medication Compliance
- 8) Anorectal Sensory and High Resolution Anorectal Manometry Testing: First sensation of rectal filling, urgency, and pain, basal anal resting pressure, voluntary anal squeeze pressure, and the rectal-anal inhibitory reflex (RAIR) to rectal distention and simulated strain, as well as the ability to evacuate a 50 cc volume rectal balloon within one minute.
- 2.18 Describe the statistical approaches that will be used to analyze the study data.
  - \* Addressed below:

Categorical data will be analyzed using Fisher's Exact tests for differences in proportions. Continuous data will be analyzed using Student's t-tests to detect differences in group means, with Bonferroni correction for multiple comparisons. We will use logistic regression to determine the factors that predict treatment responses.

A p<0.05 will be used as the threshold for statistical significance in all cases.

POWER ANALYSIS/SAMPLE SIZE: It is generally regarded that a 3-point reduction represents a clinically meaningful change using such a 10 point scale, and similar research studies using patient-reported outcomes have reported standard deviations ranging around ~2.5 points. However, we do not have baseline data to estimate variance, and thus we took a conservative estimate with an expected standard deviation of 4 points. Given these assumptions, we will need 28 patients in each study arm to detect at least a 30% reduction in symptom severity, with a power of 0.80, alpha=P<0.05 in a two-tailed analysis.

[reviewer notes-]

- 2.19 Will this research be conducted in (a) a foreign country and/or (b) at a site (e.g., Navajo Nation) where the cultural background of the subject population differs substantially from that of Pittsburgh and its surrounding communities?
  - \* No

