If the subject withdraws from the study after having passed Phase 1 (i.e. baseline measures of bowel dysfunction and quality of life), we would keep the data for an "intention-to-treat" analysis (with the assumption of an non-response). If a subject has not completed Phase 1, then the research data will be destroyed.

**5.17** Following the required data retention period, describe the procedures utilized to protect subject confidentiality. (e.g., destruction of research records; removal of identifiers; destruction of linkage code information; secured long-term retention)

We will destroy primary research records with any identifiers, but may opt to retain deidentified electronic data on a secured server for future re-analysis. Per University of Pittsburgh guidelines, research records will be archived for a minimum of seven years after final reporting or publication of a project.

Section: Section 6 - Costs and Payments

[reviewer notes-]

6.1 Will research subjects or their insurance providers be charged for any of the procedures (e.g., screening procedures, research procedures, follow-up procedures) performed for the purpose of this research study?

Yes; charges will be billed only for procedures performed as part of the subject's routine clinical care as addressed in question 2.9

[reviewer notes-]

6.2 Will subjects be compensated in any way for their participation in this research study?

\* No

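### Aim 2 screens 17 or 18 measures as predictors of response at an uncorrected p<0.05, with about two or fewer patients in the smaller outcome group per candidate

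*Combined protocol and SAP*

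**What the plan says.** Section 1.2, Aim 2, lists baseline and on-treatment symptom severity, quality of life, daily diaries, anorectal testing and (in completers) medication compliance. It then states: "All of these measures will be used to explore factors that are associated with treatment response". The verb there is exploratory, but the title of Aim 2 speaks of determining predictors, and so does item 2.18: "We will use logistic regression to determine the factors that predict treatment responses". Item 2.18 sets the criterion: "A p<0.05 will be used as the threshold for statistical significance in all cases".

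The only multiplicity rule stands in the sentence on continuous data: "Continuous data will be analyzed using Student's t-tests to detect differences in group means, with Bonferroni correction for multiple comparisons". Nothing extends it to the regression. The plan gives no list of covariates, no selection rule, no limit on their number and no validation step. It does not say whether factors are tested one at a time or together. Items 2.18 and 3.12 justify the sample size only for a difference in mean severity ratings.

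On withdrawals, item 5.16 keeps patients who leave after Phase 1 in the intention-to-treat analysis "with the assumption of an non-response".

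**The concern.** A regression that may draw on every collected measure, read at an uncorrected 5% level, has a false-positive rate far above 5% for the aim as a whole. With so few patients per candidate, ordinary maximum-likelihood logistic regression is also unreliable, and a fitted model will look more discriminating than it is. The practical risk is that Aim 2 reports a predictor of response that is a chance finding, or one that reflects who left the study. Readers would then take it as knowledge about which patients benefit, which the abstract names as a purpose of collecting these data.

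**Working it through.** **1. The plan's own figure.** Item 3.12 uses a difference of 3, an SD of 4, two-sided alpha 0.05 and power 0.80. n per arm = 2 × (1.960 + 0.842)² × 4² / 3² = 27.9, so 28 per arm and 56 in total; 56 / 0.8 = 70. The stated numbers reproduce. No corresponding figure exists for the predictor analysis.

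**2. Number of candidates** (item 2.6, Study Measures):

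| Source | Count |
|---|---|
| Severity rating ("how would you rate the severity of your bowel symptoms over the past 2 weeks") | 1 |
| Diary summaries ("abstract BM and FI weekly frequency, as well as the mean change in stool consistency") | 3 |
| PAC-SYM, FISI, PAC-QOL, FIQL, SF-36, one score each | 5 |
| Compliance | 1 |
| First sensation, urgency, pain, resting pressure, squeeze pressure | 5 |
| RAIR to distention and to simulated strain | 2 (1 if taken together) |
| Balloon evacuation | 1 |
| Total | 18 (17) |

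This leaves out questionnaire subscales, treatment arm and the demographic and MS data in item 2.14.

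**3. Separate tests, no true predictor.** If the tests are independent, P(at least one p<0.05) = 1 − 0.95^k. For k = 18 this is 0.603, for k = 17 it is 0.582. The expected number of false positives at k = 18 is 18 × 0.05 = 0.9. The measures are unlikely to be independent, and the documents give no correlations, so a common correlation has to be assumed. Large-sample draws with k = 18 give:

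| Common correlation | P(at least one) |
|---|---|
| 0 | 0.605 |
| 0.2 | 0.554 |
| 0.3 | 0.510 |
| 0.5 | 0.399 |
| 0.7 | 0.279 |

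Simulated logistic fits at 70 patients and 40% response give, at correlation 0.3, 41-46% with Wald tests and 53-54% with likelihood-ratio tests. At correlation 0.5 the figures are 31-40% with Wald tests and up to 42% with likelihood-ratio tests. With independent factors they run from 55% to 66%. Roughly 30-60% is a fair summary.

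**4. One joint model with all 18, no true predictor.** At 70 patients and 28 responders, Wald tests give 0.722, 0.695 and 0.725 at correlations 0, 0.3 and 0.5. The correlation hardly matters, because the error per coefficient is itself about 8.5% instead of 5%. Likelihood-ratio tests at correlation 0.3 give 78%. Over response rates of 30-60% the range is 67-68% (Wald) and 76-80% (likelihood ratio). Allowing for variation between simulations, about 65-80% is a fair summary. The apparent AUC of this model is 0.80-0.84 although nothing predicts.

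**5. Events per candidate.** The documents state no response rate, so a range is shown for 70 patients:

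| Assumed response | Responders | Smaller group | Smaller group / 18 |
|---|---|---|---|
| 20% | 14 | 14 | 0.8 |
| 30% | 21 | 21 | 1.2 |
| 40% | 28 | 28 | 1.6 |
| 50% | 35 | 35 | 1.9 |
| 60% | 42 | 28 | 1.6 |

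The ceiling is 35 / 18 = 1.9, or 35 / 17 = 2.1, at any response rate.

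**6. Withdrawals as non-responders.** At the planned drop-out, 0.20 × 70 = 14 patients. If half of the remaining 56 respond (assumed), there are 28 responders and 42 non-responders, and 14 / 42 = one third of the non-responders are withdrawals. Now take a factor unrelated to response but linked to leaving, with assumed drop-out of 31% with the factor and 9% without. Response is 0.5 × 0.69 = 0.345 against 0.5 × 0.91 = 0.455. The odds ratio is (0.345 / 0.655) / (0.455 / 0.545) = 0.63. The direction follows from the rule in 5.16; the size depends on the assumed rates.

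**7. Timing of the candidates.** Compliance is assessed only in completers, and change in stool consistency is measured over the treatment period. Neither is known at baseline, so neither can predict response in the usual sense.

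**The case against.** Several objections have weight.

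- A reader might infer that the plan will more likely than not name a false predictor. The documents do not support this in general. It is firm only if all measures enter one model, and the plan does not say so. For separate tests the chance falls to about one half or below once the common correlation reaches about 0.3, and overlap between, for example, PAC-SYM and PAC-QOL makes such correlations plausible. All these probabilities also assume that no measure is truly associated with response, while sections 1.2 and 1.3 give mechanistic reasons why some might be.
- A reader might take 28 as the expected number of responders. The only 28 in the documents is patients per arm. As a responder count it needs an assumed 40% response in 70 patients. The ceiling in step 5 does not need that assumption.
- The withdrawal problem and the full model cannot both apply in full. A complete-case model containing compliance drops the withdrawals, so the distortion in step 6 largely goes. But that model has at most 56 patients and at most 28 in the smaller group (28 / 18 = 1.6), and with 28 responders the joint-model figure is 77% (Wald). Either route has a problem, and the plan does not choose between them.
- Withdrawal as non-response is pre-specified, so a factor that predicts leaving does predict the outcome as defined. That is true, but it is then not evidence about bowel response, and only a repeat in observed patients separates the two.
- Aim 2 is secondary and uses exploratory language. This lowers the importance. It does not remove the fault, because 2.18 applies the p<0.05 criterion to every analysis and speaks of determining predictors.

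**Conclusion.** The concern holds for the predictor analysis in Aim 2. Followed as written, the plan tests 17 or 18 candidates with no correction stated for the regression. The chance of at least one false predictor is roughly 30-60% with separate tests and about 65-80% in one joint model, against a nominal 5%. These figures rest on no true association, on assumed correlations of 0 to about 0.7 for separate tests (0 to 0.5 for the joint model), and on the choice of test. The limit of about two events per candidate rests only on 70 patients and the count of measures. The effect of treating withdrawals as non-responders is certain in direction if leaving depends on the factor; its size is not known.

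Two further inferences go too far. The primary comparison of arms is not touched by any of this. And although section 1.2 hopes to support a treatment algorithm, no passage says that predictors from Aim 2 will be used to select patients. This is a change that should be made to a secondary analysis, not a threat to the trial's main result.

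**What to change.** In item 2.18:

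1. Name a short list of baseline candidates, about three, drawn from the mechanism that the protocol itself describes; symptom type, a rectal sensory threshold and balloon evacuation are examples. At an assumed 28 responders, three single-coefficient terms give 28 / 3 = 9.3 events each; at 14 responders, 4.7. A factor with more than two categories uses more than one coefficient.
2. Fit them with a penalised logistic regression (Firth is one option), or model the week-4 rating on its 1-10 scale directly. The exact number of candidates and the type of penalty are for the trial statistician to settle before unblinded data are seen.
3. Report all other measures, including compliance and on-treatment diary change, with estimates and confidence intervals only, labelled hypothesis-generating and exempt from the p<0.05 criterion.
4. Repeat the model in patients with an observed week-4 rating, beside the analysis that counts withdrawals as non-responders.

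Extending Bonferroni to the regression would not be enough. For 18 independent separate tests it restores the overall error to about 4.9% (1 − (1 − 0.05/18)^18), but it leaves the shortage of events per candidate and the withdrawal problem as they are.

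The cost is analysis wording only: no added patients, visits or data. The downside is that fewer factors can be called predictors.

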# 1.3 Background: Briefly describe previous findings or observations that provide the background leading to this proposal.

There is growing recognition that the factors driving multiple sclerosis (MS)-related disability extend beyond impairments in mobility to include both psychological and physical symptoms that negatively impact patients' quality of life. Anorectal dysfunction, broadly defined as the presence of chronic constipation and/or fecal incontinence, is a common symptom experienced by MS patients that is often ranked as negatively impactful on quality of life as impaired mobility. About 40% of MS patients suffer from chronic constipation, while ~25% of patients experience frequent episodes of fecal incontinence. Mixed forms of anorectal dysfunction are less common, occurring in at least 10-15% of MS patients, but pose a particular therapeutic challenge. Because of the daily impact of these common symptoms, anorectal dysfunction places a tremendous burden on MS patients and their caregivers.

Normal defecation patterns require precise conscious and unconscious sensorimotor functions to support the perception of rectal filling, to retain stool in the rectum without anal leakage, and to allow for volitional elimination of stool without difficulty. MS patients may be especially prone to developing anorectal dysfunction because even subtle impairments in sensation from the anorectum and/or the timing and efficacy of coordinated abdominal, pelvic floor, and anal muscle contractions are sufficient to generate symptoms. Regardless of subtle differences in the underlying mechanisms that lead to anorectal dysfunction in any one MS patient, an ideal therapeutic approach should be safe, flexible, straightforward, and effective enough to help most patients.

# 1.4 Significance: Why is it important that this research be conducted? What gaps in existing information or knowledge is this research intended to fill?

Despite its significant burden on MS patients, there remains a paucity of published studies to provide strong evidence for any specific therapeutic option for anorectal dysfunction in this population. The few available studies are mostly small, uncontrolled trials, including studies focused on behavioral interventions and biofeedback, which demonstrated some limited benefit restricted to those with mild MS disease. This finding may not be surprising, as biofeedback requires intact central neural control over motor systems that are likely to be disrupted in MS patients with more advanced disease and more severe forms of anorectal dysfunction. Although abdominal massage may improve constipation in MS patients, this intervention is time consuming and difficult for MS patients with advanced disease to accomplish. Transanal irrigation in MS patients with anorectal dysfunction showed some promise of benefit in a substantial number of patients, but this approach requires specialized equipment, can be cumbersome for patients and caregivers to implement and poses some inherent risk of colonic perforation. Therefore, there is compelling need to establish evidence supporting a safe, effective, and easily implemented

Section: Section 1 - Objective, Aims, Background and Significance

treatment option for anorectal dysfunction in MS patients.

One strategy often used in routine clinical practice to manage anorectal dysfunction is to normalize stool form while providing a means for "timed rectal evacuation" using a stimulant laxative rectal suppository. The benefit of this dual approach is to both minimize the difficulties with evacuation and to allow patients some flexibility in planning their schedule. With regular emptying of the distal colorectum, patients should be able to avoid rectal fecal impaction and minimize episodes of fecal incontinence. However, such a practical approach to anorectal dysfunction, particularly regarding the use of timed rectal evacuation, has not been subjected to rigorous clinical evaluation. The goal of this proposal is to determine the efficacy of timed rectal evacuation in an algorithm-based bowel regimen for treating anorectal dysfunction in patients with mild-to-moderately severe MS.

Section: Section 2 - Research Design and Methods

[reviewer notes-]

- 2.1 Does this research study involve the use or evaluation of a drug, biological, or nutritional (e.g., herbal or dietary) supplement?
  - \* Yes
- 2.1.1 Does this research study involve an evaluation of the safety and/or effectiveness of one or more marketed nutritional (e.g., herbal or dietary) supplements for the diagnosis, prevention, mitigation or treatment of a specific disease or condition or symptoms characteristic of a specific disease or condition?
  - \* No

[reviewer notes¬]

- 2.1.2 Does this research study involve the use or evaluation of one or more drugs or biologicals not currently approved by the FDA for general marketing?
  - \* No

[reviewer notes-]

- 2.1.3 Does this research involve the use or an evaluation of the effectiveness and/or safety of one or more drugs or biologicals currently approved by the FDA for general marketing?
  - \* Yes
- 2.1.3.1 Are the FDA-approved drugs or biologicals being evaluated in this research study for a new clinical indication, different population, or route of administration and/or dosage level that is not currently specified in the FDA-approved product labeling?

Drugs are often used **Off-Label** during routine practice. Before answering this question, review the FDA product labeling (http://labels.fda.gov) for the approved "Indications and Usage." If being used off-label, answer **Yes** to this question. You are required to provide

information and/or upload the package insert for each drug that is administered for research purposes.

\* No

If you respond **YES**, an IND number or the FDA written concurrence of IND exemption may be required.

Upload information on FDA approved indications/doses and FDA exemption letter if applicable:

Name Modified Date

[reviewer notes¬]

- 2.2 Will this research use or evaluate the safety and/or effectiveness of one or more devices?
  - \* No

[reviewer notes¬]

2.3 Summarize the general classification (e.g., descriptive, experimental) and methodological design (e.g., observational, cross-sectional, longitudinal, randomized, open-label single-blind, double-blind, placebo-controlled, active treatment controlled, parallel arm, cross-over arm) of the proposed research study, as applicable.

Single-center, randomized, double-blind placebo controlled clinical trial

